6.7 Other Trial Devices

YSI 2300 STAT Plus™ (Yellow Springs Instruments): The YSI 2300 STAT Plus is an FDA-approved glucose analyzer. Blood glucose measurements using the YSI 2300 STAT Plus will be obtained off of the intravenous (IV) line during both treatment visits.

Nova Biomedical StatStrip Xpress Glucose Meter: The Nova StatStrip Xpress glucose meter is an FDA-approved glucose meter that is commercially available. Blood glucose measurements for CGM calibration will be obtained with the Nova StatStrip Xpress during both treatment visits if the YSI 2300 STAT Plus fails and via fingerstick with the Nova StatStrip Xpress during any periods when IV blood samples are not available for any reason or the IV fails.

Exercise Bike: The trial will utilize a stationary exercise bike (ergometer) for the in-clinic exercise at the treatment visits. This bike will be stored at the Diabetes Research Center when not in use.

6.8 Concomitant Medications

6.8.1 Permitted Medications and/or Procedures

Patients may take any over-the-counter medications that they wish during the trial, with the exception of any medication containing acetaminophen as that may cause interference with CGM sensing. All concomitant medications, including over-the-counter medications, should be recorded.

Use of beta blockers will be allowed as long as the dose is stable and the patient does not meet the criteria for hypoglycemia unawareness while taking that stable dose.

If patients experience urgent or emergent medical concerns outside the scope of diabetes care and their primary care physicians, they will be taken to the MGH walk-in clinic or emergency room, or if necessary call 911.

Clinical Trial Protocol
ZP4207-16051

Version number: 8.0
Amendment 7.0
Date: 06 January 2017

6.8.2 Excluded Medications and/or Procedures

During the trial, patients will not use any recreational drugs or drugs of abuse. The need to take prescription drugs that dull the sensorium, reduce sensitivity to symptoms of hypoglycemia, or hinder appropriate decision-making may be grounds for exclusion from the trial or discontinuation of participation, a decision that will be made by the Investigator.

Use of benzodiazepines or narcotics, even if by prescription, may be excluded according to the judgment of the Investigator. Use of oral anti-diabetic medications (e.g., thiazolidinediones, biguanides, sulfonylureas, glitinides, DPP-4 inhibitors, SGLT-2 inhibitors) will also be excluded.

7 TRIAL PROCEDURES

7.1 Informed Consent

After potential patients have had time to review the consent document, and prior to any trial-related activities, they will meet with a trial MD or designee who will explain the trial, answer any questions, and administer informed consent. In the event that a volunteer is a patient of 1 of the trial MDs, another staff MD or designee will answer questions and administer consent. The patients will be fully informed of their responsibilities and their rights while participating in the trial as well as of the possible risks and potential benefits of participation in the trial. They will have the opportunity to discuss all questions and ample time to consider participation.

Trial-related activities are any procedures that would not have been performed during normal management of the patient. Patients who wish to participate in the trial will be asked to personally date and sign an informed consent form (ICF). Likewise, the Investigator must also personally date and sign the ICF. All patients will be provided with a copy of their own signed and dated ICF.

Trial staff will answer any questions that the patients may have during their participation. They will share any new information in a timely manner that may be relevant to the patient's willingness to continue participating in the trial. The patients may choose to discontinue their participation at any time.

7.2 Screening Visit (Visit 1)

All patients will have a Screening Visit to confirm eligibility. The patient will be interviewed and the electronic Case Report Form (eCRF) will be completed by trial staff to establish whether the patient is eligible.

Patients will be instructed concerning diabetes management (e.g., basal insulin rate adjustment by insulin pump) during fasting prior to and between the treatment visits per the medical judgment of the Investigator.

Once all of the results have been returned, a trial MD will review the eCRF to determine patient eligibility. If a patient is not eligible to continue in the trial, the results of abnormal tests will be reported to the patient and to a health care provider of their choosing.

Clinical Trial Protocol
ZP4207-16051

Version number: 8.0
Amendment 7.0
Date: 06 January 2017

7.2.1 **Data Collected at Screening**

- Age, sex, race, and ethnicity
- Date of last menstrual period in female patients
- Medical, surgical, and social history, allergies, and review of systems relevant to inclusion and exclusion criteria, including:
 - Date of diabetes diagnosis
 - Duration of insulin pump use and type of insulin used in pump
 - Type/model of insulin pump
 - Insulin regimen (basal rate, sensitivity factor, and carbohydrate ratio)
 - Average total daily dose of insulin in the last 30 days as available (from pump history)
 - Usage of CGM, if any (type of CGM, days per month worn, usage of data, whether insulin is dosed based on CGM alone, alarm settings)
- Concomitant illness (any illness present at screening)
- Concomitant medications (prescription and non-prescription) and date of last change in medication regimen
- Height, weight, physical examination, and vital signs including body temperature and blood pressure
- Orthostatic vital signs (heart rate and blood pressure) in the seated position and within 3 minutes of standing
- 12-lead ECG
- Hemoglobin A1c
- Chemistry and hematology samples (see [Appendix B](#))
- Urine HCG pregnancy test for women of childbearing potential
- FSH level for postmenopausal women amenorrheic for less than 1 year
- Fractionated plasma metanephrines (if indicated by history)

7.3 **Training Visit (Visit 2)**

A Training Visit will take place before the first treatment visit. Patients will be trained in the insertion and calibration of the Dexcom G4 sensor and trial policies and procedures. Trial staff will verify that the patients have understood the material and are competent to participate safely in the trial. Concomitant medications will also be reviewed.

Patients will be instructed concerning diabetes management (e.g., basal insulin rate adjustment by insulin pump) during fasting prior to and between the treatment visits per the medical judgment of the Investigator. The goals of diabetes management for patients during the fasting period are to avoid hypoglycemia, to treat hypoglycemia if it occurs, and to arrive at the treatment visit in the morning with a BG between 80 and 250 mg/dL. If insulin pump basal rates are properly configured, patients should be able to fast from 12:00 AM until the time of arrival for the visit without a high likelihood that they will become hypoglycemic or severely hyperglycemic. Patients will be asked whether they believe that they can safely fast from 12:00 AM until their arrival time at approximately 7:00 AM without adjusting their basal rates. If they have concerns, a trial physician will consult with them regarding pump basal rate adjustments. In all cases, subjects will be instructed to self-treat with carbohydrates according to the 15/15 rule (15 grams of carbohydrates, repeated in 15 minutes if necessary) during the overnight fasting period and at any time prior to their arrival at the trial site for the treatment visits.

Clinical Trial Protocol
ZP4207-16051

Version number: 8.0
Amendment 7.0
Date: 06 January 2017

7.4 Treatment Visits (Visit 3 and Visit 4)

- Visit 3 will take place at least 48 hours after screening (Visit 1) and no more than 30 days after screening (Visit 1).
- There will be a 24-hour minimum washout between Visit 3 and Visit 4 and a maximum of 3 weeks between Visit 3 and Visit 4.
- Up to 2 patients may participate per day.
- In Part 1, each patient will participate in 2 treatment visits: 1 with the iPhone-based BP using ZP4207 and 1 with the iPhone-based BP using Lilly glucagon in a randomized order.
- In Part 2, each patient will participate in 2 treatment visits: 1 with the iLet using ZP4207 and 1 with the iLet using Lilly glucagon in a randomized order.
- The night before the treatment visit, patients will place a Dexcom G4 CGM sensor in the abdominal skin and calibrate the sensor when prompted using the provided Nova StatStrip Xpress meter. Patients will be instructed to call if they encounter any difficulty with their CGM.
- Patients will be responsible for their own medications other than insulin during the trial. Any medical advice needed by the patients during their participation that is not directly related to BG control should be obtained from them in their usual manner. Patients may take any over-the-counter medications that they wish during the trial, with the exception of any medication containing acetaminophen as that may cause interference with CGM sensing. If patients experience urgent or emergent medical concerns outside the scope of diabetes care and their primary care physicians, they will be taken to the MGH walk-in clinic or emergency room, or if necessary call 911.
- During the trial, patients will not use any recreational drugs or drugs of abuse. The need to take prescription drugs that dull the sensorium, reduce sensitivity to symptoms of hypoglycemia, or hinder appropriate decision-making may be grounds for exclusion from the trial or discontinuation of participation, a decision that will be made by the Investigator.
- Patients will be instructed concerning diabetes management (e.g., basal insulin rate adjustment by insulin pump) during fasting prior to and between the treatment visits per the medical judgment of the Investigator.
- Patients will not tamper with the BP, including changing any settings.
- Patients may not remove the BP during the trial unless the BP failed or they are withdrawing from the trial.
- The exact time of each procedure and assessment will be documented.

7.4.1 Visit Procedures

- Patients will be asked to arrive at the visit at least 1 hour in advance of the start of the BP having fasted since 12:00 AM the night before (treatment with simple carbohydrate of up to 30 g for a low is allowed). If the patient is not fasted, the visit will be rescheduled within the visit window. If BG is >250 mg/dL, the visit will be rescheduled within the visit window. If BG is <50 mg/dL, the patient will be treated with simple carbohydrate according to the 15/15 rule (15 grams of carbohydrates, repeated in 15 minutes if necessary). The visit will not need to be rescheduled unless the patient experiences a severe hypoglycemic event and requires treatment with glucagon or IV dextrose. If the visit needs to be rescheduled due to hypoglycemia or hyperglycemia, trial staff will assist the patient with insulin or medication adjustments to address glycemic control.

Clinical Trial Protocol
ZP4207-16051

Version number: 8.0
Amendment 7.0
Date: 06 January 2017

- The patient will be instructed to contact trial staff later in the day if his or her BG remains uncontrolled.
- Upon arrival to the visit, the patient's weight and vital signs including body temperature and blood pressure will be documented.
 - Orthostatic vital signs (heart rate and blood pressure) will be measured in the seated position and within 3 minutes of standing.
 - Patient reports of symptoms, any other complaints, and AEs will be reviewed.
 - Concomitant medications will be recorded.
 - Chemistry and hematology samples will be collected at visit start (see [Appendix B](#)).
 - ADA samples will be collected before the start of dosing (Visit 3 only).
 - A 12-lead ECG will be performed.
 - A urine HCG pregnancy test will be performed in female patients of childbearing potential. If the test is positive, the patient will be informed of the result and the visit will be ended.
 - Patients will complete a baseline survey about their attitudes and experience with their usual diabetes care.
 - An IV catheter will be placed for blood sampling.
 - Trial staff will assist the patient to calibrate their CGM, review the trial procedures again and assist with the setup of the BP system, including inserting and priming infusion sets.
 - The control algorithm will be initialized only with the patient's weight. Diagnostics will be performed to ensure that the CGM device is appropriately calibrated and that all of the components of the BP systems are in working order.
 - The basal rate of the patient's own insulin infusion pump will be changed to be 2-fold higher than weighted mean of the basal rate during the trial period. This is intended to increase the usage of glucagon during the treatment visit. The basal insulin rate may be decreased during the treatment visit at the discretion of the Investigator. To the extent possible, the same basal rate should be used at Visit 3 and Visit 4.
 - The patients will continue to wear their own infusion pump infusing at the temporary basal rate throughout the visit until the start of the structured exercise period, in addition to the BP.
 - The staff will start the BP as close as possible to a minute divisible by 5 minutes (i.e., on a 5-minute mark). The starting time will be considered Hour 0.
 - Additional calibrations will be performed at any of the BG checks throughout the day if the CGM value does not meet the ISO standard (<15 mg/dL difference for BG values <75 mg/dL; <20% absolute difference for BG values >75 mg/dL) at the time of the BG measurement AND it is a good time to calibrate (the CGM trend arrow is flat and there has been no carbohydrate intake in the last 30 minutes or glucagon boluses in the last 15 minutes).
 - Blood samples will be taken from the IV at least hourly and processed for plasma ZP4207/glucagon. If BG is <150 mg/dL, more frequent samples for plasma ZP4207/glucagon may be drawn at the discretion of the Investigator. The actual time of sampling will be recorded in the eCRF.
 - Plasma glucose samples will be taken from the IV at least hourly in parallel with ZP4207/glucagon exposure sampling and measured using the YSI 2300 STAT Plus. If the YSI 2300 STAT Plus and/or IV fails, the Nova StatStrip Xpress will be used for glucose measurements. If BG is <150 mg/dL, then sampling will be every 30 minutes. If BG is <100 mg/dL, then sampling will be every 20 minutes. If BG is <80 mg/dL, then

Clinical Trial Protocol
ZP4207-16051

Version number: 8.0
Amendment 7.0
Date: 06 January 2017

sampling will be every 10 minutes. The actual time of sampling will be recorded in the eCRF.

- Patients will be asked to rate any nausea and/or infusion site pain on 10 cm visual analog scales (VAS) at the beginning of the visit once the infusion sites have been placed but no drug has yet been administered, then approximately at the top of every hour during the visit, and at the end of the visit. Trial staff will also evaluate their infusion sites to document any erythema or edema at the same times. If moderate or severe pain is reported or swelling or redness occurs at the infusion site, the infusion site will be replaced in a different location. If moderate or severe pain, swelling, or redness continues at the old site for more than 30 minutes after the infusion site is removed, or if moderate or severe pain, swelling, or redness occurs at the new site, all infusion sites will be removed and the patient will be discontinued from the study. Any such symptoms will be followed until resolution.
- From the start of closed loop control until approximately Hour 3, the patients will continue to fast.
- Between approximately Hour 3 and Hour 4, patients will be provided with a lunch meal of their choice in the Diabetes Research Center from a menu of choices from nearby restaurants. They will be asked to choose a meal that is a “typical meal” for them. The content of their meal will not be restricted in any way, with the exception that the number of carbohydrates should be in the “typical” range for them at lunch, and that they must eat the same meal at the same time during both visits.
- At approximately 15 minutes before the meal, patients will administer a bolus for the meal with their own insulin pump based on the carbohydrate count for the meal in agreement with the Investigator.
- After lunch is completed, the patients will not be allowed any carbohydrate intake (non-caloric drinks will be permitted) until the trial is completed (except as necessary to treat hypoglycemia), to allow the BP to control the post-prandial BG without further interruption.
- Between approximately Hour 6 and Hour 7, the patients will start a period of structured exercise.
- At the start of the exercise period, patients will restore their normal basal insulin profile so that they will not have elevated insulin levels at the end of the study period when they are to transition back to their usual care.
- Patients will exercise on a stationary bike with a heart rate from 120-140 beats per minute for a total of 4,000 heart beats (approximately 30 minutes). Patients will rate their exercise intensity using the Borg scale every 5 minutes, with the target intensity level between 12 and 14. Heart rate will be measured every 5 minutes.
- Chemistry and hematology samples will be collected immediately after end of exercise (see [Appendix B](#)).
- BG measurements will be obtained off of the IV line every 10 minutes. If BG is <80 mg/dL, BG measurements will be obtained off of the IV line every 5 minutes.
 - If BG is <50 mg/dL, the exercise will be terminated regardless of heart beats achieved.
 - Carbohydrates will be given for any BG <50 mg/dL according to the following protocol: Dextrose (g) = BSA (m²)/[1.7 m² (women) or 1.9 m² (men)] *15 g.
 - Repeat treatments will be given at 15-minute intervals as long as BG remains <50 mg/dL.

Clinical Trial Protocol
ZP4207-16051

Version number: 8.0
Amendment 7.0
Date: 06 January 2017

- If there is an interruption in the Dexcom CGM output, trial staff will assist the patient in recovering CGM data streaming. If this requires replacement of the CGM sensor, BGs will be checked every 10 minutes (every 5 minutes if BG is <80 mg/dL) using blood from the IV until the CGM is able to be calibrated again. These BGs will be entered into the BP, which will treat them as CGM values and dose insulin and/or glucagon appropriately.
- If there is a complete failure of the BP operation, patients will take over their own BG control using their personal insulin pump until the BP can be brought back online. If BP control cannot be promptly resumed (e.g., within 30 minutes), the patient may be asked to repeat that trial day once.
- Patients may choose to withdraw from the trial at any time. If they withdraw from the trial, they should alert a provider immediately.
- Just prior to the end of the study visit, vital signs including body temperature and blood pressure will be obtained and a 12-lead ECG will be performed. Orthostatic vital signs (heart rate and blood pressure) will be measured in the seated position and within 3 minutes of standing. If patients have hypotension or orthostatic hypotension, discharge will be delayed until their blood pressure is normal and stable.
- After approximately Hour 8, but not earlier than at least 60 minutes after end of exercise, the BP will be stopped and the patient will continue with their personal insulin pump.
- If the patient experiences seizure or unconsciousness, persistent nausea or vomiting, diabetic ketoacidosis, persistent hyperglycemia with ketonemia, hemodynamic changes such as hypotension, or other medically significant findings, a longer observation period at the trial site may be necessary until the patient is considered stable for discharge. If the Investigator or trial staff determines that the patient requires further observation or treatment, the patient may be transferred to the emergency room for additional monitoring and/or medical care. At discharge, patients will be provided with any necessary instructions concerning personal insulin pump usage, food intake, and driving arrangements.
- The maximum amount of blood loss per study visit will be approximately 230 mL. The total blood loss for the entire study will be up to 460 mL.
- The BP and glucose meters will be collected and downloaded.
- A trial MD will review the last several hours of insulin and glucagon dosing and assist the patient in resuming their usual diabetes care. A longer observation period at the trial site may be necessary. Patients will be instructed to call trial staff with any questions, issues, or concerns.

7.4.2 Data Collected During the Treatment Visits

- CGM glucose every 5 minutes from the Dexcom G4 Platinum CGM
- All BG measurements taken
- Insulin total dose by the BP and the patient's own insulin pump
- Glucagon total dose
- Timing and content of the meal eaten and carbohydrate amount
- Timing of meal announcement and size of meal announced
- Timing and glucose values at calibrations
- Timing and amount of carbohydrates taken for hypoglycemia
- Time patients were not under BP control for any reason
- List of technical faults associated with the BP including cause and resolution

Clinical Trial Protocol
ZP4207-16051

Version number: 8.0
Amendment 7.0
Date: 06 January 2017

- ZP4207/glucagon sampling will be collected at least hourly. If BG is <150 mg/dL, more frequent samples for plasma ZP4207/glucagon may be drawn at the discretion of the Investigator.
- Plasma glucose sampling will be collected at least hourly in parallel with ZP4207/glucagon exposure sampling. If BG is <150 mg/dL, then sampling will be every 30 minutes. If BG is <100 mg/dL, then sampling will be every 20 minutes. If BG is <80 mg/dL, then sampling will be every 10 minutes.
- Nausea and infusion site pain on a VAS at visit start (after insertion and before any drug administration), hourly, and at visit end
- Infusion site reaction according to the Draize scale at visit start (after insertion and before any drug administration), hourly, and at visit end
- Patient reports of symptoms, any other complaints, and AEs
- Vital signs including body temperature and blood pressure (at visit start and visit end) and weight
- Orthostatic vital signs (heart rate and blood pressure) in the seated position and within 3 minutes of standing
- Concomitant medications
- Chemistry and hematology samples (see [Appendix B](#)) at visit start and immediately after end of exercise
- ADA (Visit 3 only)
- 12-lead ECG at visit start and visit end
- Urine HCG pregnancy test for women of childbearing potential

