The Phase 1 results did not give rise to specific safety concerns, beyond those related to the pharmacological effect of ZP4207. All adverse events (AEs) recorded in the trials were of mild or moderate severity. The most frequent systemic AE related to treatment with ZP4207 was nausea, which is a known side-effect following administration of glucagon. The most frequent injection site reaction was transient erythema, occurring in all ZP4207, glucagon, and placebo treatment groups, irrespective of dose. No anti-drug antibodies (ADA) incidences were observed.

The observed PD response, in terms of increased plasma glucose, in insulin-induced hypoglycemic patients with T1DM following dosing with 0.7 mg ZP4207 administered IM was similar to that observed following IM dosing with 1.0 mg glucagon (GlucaGen, Novo Nordisk). An increase in plasma glucose of ≥ 20 mg/dL from hypoglycemic levels was achieved within 30 minutes for all patients.

In terms of PK, ZP4207 had a short half-life and high clearance and dose proportionality for both maximum plasma concentration and area under the concentration-time curve from time 0 to 300 minutes in the dose range 0.1 to 2.0 mg following SC administration. Following IM administration, dose proportionality was shown in the investigated dose range of 0.3 to 2.0 mg. The PK properties of 0.7 mg ZP4207 IM were comparable with those of 1.0 mg glucagon (GlucaGen, Novo Nordisk) with IM administration.

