Treatment with ZP4207 and marketed glucagon can result in undesired effects or complaints. Undesired effects and complaints such as gastrointestinal side effects including nausea, vomiting, and diarrhea are known side effects of glucagon administration at higher dose levels. The frequency of nausea associated with the administration of 1 mg of glucagon according to the Summary of Product Characteristics (SPC) for Glucagon is described to be between 1/10 and 1/100. The frequency of vomiting is described to be between 1/100 and 1/1000 (Novo Nordisk, 2015). Similar gastrointestinal side effects have also been observed to a limited degree in the 2 clinical trials conducted with ZP4207, again at higher dose levels. The individual doses of ZP4207 and Lilly glucagon delivered by the BP are expected to be significantly lower than doses typically associated with nausea. Episodes of low blood pressure have also been observed after administration of higher doses of glucagon and ZP4207. As with every novel drug substance, new and yet unknown side effects may also occur.

There are limited data available to describe the immunogenic potential of glucagon products available on the market, but the data available indicate that marketed glucagon only has a small immunogenic potential. A Phase 1 trial performed with recombinant human glucagon and animal derived glucagon in 75 healthy patients did not show signs of ADA measured 13 weeks after trial product administration (Eli Lilly, 2005). In the ZP4207 FHD trial, ZP4207-14013, no confirmed anti-ZP4207 or anti-glucagon antibodies were detected in any of the samples. In addition, the 5 sequential administrations of ZP4207, as applied in trial ZP4207-15007, were not associated with the development of antibodies against ZP4207 in the 18 subjects enrolled to receive ZP4207. The optimized formulation of ZP4207, as applied in the present trial is not expected to change the immunogenic potential of the Investigational Medicinal Product (IMP).

In relation to diabetes therapy, development of insulin-antibodies is documented more substantially and route of administration has been shown to influence immunogenic potential of insulins. However, these antibodies against insulin generally do not have an impact on insulin action and are thus not clinically relevant.

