 9. Vital signs including body temperature and blood pressure will be obtained at visit start and visit end. Blood pressure and heart rate will be measured in the seated position and within 3 minutes of standing.
 10. At visit start and immediately after end of exercise.
 11. Urine HCG pregnancy test only for women of childbearing potential. The date of the last menstrual period in female patients will be obtained at Visit 1 only.
 12. Test for FSH level only for postmenopausal women amenorrheic for less than 1 year.
 13. If indicated by history.
 14. Patients will be trained in the insertion and calibration of the Dexcom G4 sensor, diabetes management (e.g., basal insulin rate adjustment by insulin pump) during fasting prior to and between the treatment visits, and trial policies and procedures.
 15. Collected at least hourly. If BG is <150 mg/dL, then sampling will be every 30 minutes. If BG is <100 mg/dL, then sampling will be every 20 minutes. If BG is <80 mg/dL, then sampling will be every 10 minutes.
 16. Collected at least hourly. If BG is <150 mg/dL, more frequent samples for plasma ZP4207/glucagon may be drawn at the discretion of the Investigator.
 17. Once the infusion sites have been placed but no drug has yet been administered.
 18. Between approximately Hour 3 and Hour 4.
 19. Between approximately Hour 6 and Hour 7.
 20. Before the start of dosing.
- ADA = anti-drug antibodies; BG = blood glucose; BP = bionic pancreas; CGM = continuous glucose monitor; ECG = electrocardiogram; FSH = follicle-stimulating hormone; HbA1c = hemoglobin A1c; HCG = human chorionic gonadotropin; VAS = visual analog scale.

Clinical Trial Protocol
ZP4207-16051

Version number: 8.0
Amendment 7.0
Date: 06 January 2017

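### Blood pressure is scheduled only on arrival and at visit end, so the vital-signs component of the primary endpoint is unlikely to show short, symptomless falls during dosing

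*Protocol*

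**What the plan says.** The protocol gives the same schedule in three places. Section 7.4.2 lists "Vital signs including body temperature and blood pressure (at visit start and visit end) and weight". Footnote 9 of the schedule of procedures (Appendix A) repeats it: "Vital signs including body temperature and blood pressure will be obtained at visit start and visit end". Section 7.4.1 gives the timing. The first reading comes at the door: "Upon arrival to the visit, the patient's weight and vital signs including body temperature and blood pressure will be documented". Arrival itself is early: "Patients will be asked to arrive at the visit at least 1 hour in advance of the start of the BP". The second comes at the close: "Just prior to the end of the study visit, vital signs including body temperature and blood pressure will be obtained". At both points a postural pair is taken: "Orthostatic vital signs (heart rate and blood pressure) will be measured in the seated position and within 3 minutes of standing". If the end reading is low, discharge waits until blood pressure has recovered.

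Between those two points no blood pressure is scheduled. Heart rate is taken every 5 minutes during exercise. Nausea, infusion site pain and the Draize score are recorded at visit start, every hour and at visit end.

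Section 8.1 lists vital signs as one component of the primary safety and tolerability endpoint, and Section 11.2.1 summarises them descriptively. Section 1.5 says of both drugs: "Episodes of low blood pressure have also been observed after administration of higher doses of glucagon and ZP4207". Section 1.4 says that "ZP4207 had a short half-life and high clearance".

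**The concern.** The device can dose every 5 minutes for about 8 hours. Given the short half-life, it is reasonable to infer that any blood pressure effect could be brief and follow dosing. One reading is taken before any trial drug and the other when dosing is ending or over, so the dosing period itself is almost unobserved for this component. Nausea, pain and site reactions, which belong to the same endpoint, are followed hourly.

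What is at stake is how an unremarkable vital-signs table can be read. It would describe blood pressure before dosing and at the end of the visit. It could not support a statement that blood pressure held steady while ZP4207 or glucagon was being given, which is the period a safety comparison of the two is about.

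**Working it through.** The protocol gives no figure for this point, so there is none to reproduce. The check has two parts: the length of the unobserved gap, from the protocol's own timetable, and an illustration of what one end reading can catch.

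**Gap between readings (Sections 6.4 and 7.4.1)**

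- Exercise is 4,000 heart beats at 120 to 140 per minute: 4,000/140 = 28.6 min to 4,000/120 = 33.3 min.
- Exercise starts between about Hour 6 and Hour 7. The device stops after about Hour 8 and at least 60 min after exercise ends.
- Earliest stop: the later of Hour 8 and 6 + 28.6/60 + 1 = 7.5, so Hour 8.0.
- Latest stop on these minimum waits: the later of Hour 8 and 7 + 33.3/60 + 1 = 8.6, so Hour 8.6.
- Adding the minimum 1 hour between arrival and Hour 0 gives 9.0 to 9.6 hours between the two readings. Earlier arrival lengthens this. The end reading is taken to be at about device stop; the text does not say whether it comes before or after.
- Dosing opportunities in 8 hours: 480/5 = 96.

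**Chance of catching an episode (illustrative)**

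Assumptions, none of them in the documents: one episode per visit, lasting *d* minutes, at a random time in the 480 dosing minutes. The end reading overlaps it with probability *d*/480. Hourly readings overlap it with probability min(1, *d*/60). If each of the 10 patients in a part had one such episode, independently, the chance that the end readings show at least one is 1 − (1 − *d*/480)^10.

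| Assumed length | End reading only | Hourly readings | At least one seen in 10 patients, end reading only |
|---|---|---|---|
| 15 min | 15/480 = 3.1% | 15/60 = 25% | 27% |
| 30 min | 30/480 = 6.3% | 30/60 = 50% | 48% |
| 60 min | 60/480 = 12.5% | 100% | 74% |
| 120 min | 120/480 = 25% | 100% | 94% |

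Detection with the end reading alone is poor for short episodes and improves as they lengthen. The seated and standing pair is treated here as one time point, because both values are taken within minutes of each other.

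**The case against.** A reader might infer that the schedule cannot detect hypotension at all. The documents do not support that. The end assessment, with its standing measurement, can find a fall that is still present, and a low value delays discharge. Patient symptoms and adverse events are recorded during the visit and form another component of the same endpoint. A nurse or physician is with the patients throughout (Section 7.4.8). What remains uncovered is the short fall without symptoms.

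A reader might also infer that the plan names transient hypotension as an expected effect in this trial. It does not. Section 1.5 ties the episodes to higher doses and says nothing about how long they lasted. Section 6.4 caps a single bolus at 80 µg, against single ZP4207 doses of up to 2 mg given before (1/25 of that amount), and expects a mean daily total below 1.0 mg. This lowers the prior concern. It does not show that repeated small doses leave blood pressure unchanged, and Section 7.4.1 doubles basal insulin in order to raise glucagon use.

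It is also tempting to say that the end reading is uninformative because the doubled basal rate has ended by then. That is not established. The rate is restored at the start of exercise, but Section 1.2 gives 4 to 8 hours for clearance of subcutaneous insulin, so glucagon dosing may well continue late in the visit.

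Finally, the summary of changes for Amendment 6.0 shows that the orthostatic readings at visit start and end were introduced in an amendment responding to FDA feedback on hypotension. The risk was therefore considered, and the schedule is consistent across sections. That makes this a matter of how well the choice serves the endpoint, not of an overlooked hazard. The percentages are also fair game: they rest on an assumed length and a single episode, repeated episodes would be easier to catch, and hourly readings would still miss 50% to 75% of single episodes of 15 to 30 minutes.

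**Conclusion.** The point holds in a limited form. Followed as written, the plan leaves about 9.0 to 9.6 hours, covering nearly all dosing, without a scheduled blood pressure. The vital-signs component is therefore unlikely to show short, symptomless falls during dosing. The gap follows from the protocol's timetable. The detection probabilities (3% to 25% for the end reading, 25% to 100% for hourly readings) are illustrations for assumed episode lengths of 15 to 120 minutes.

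Nothing in the protocol says that a normal table will be reported as proof of haemodynamic safety, and the analysis is descriptive in a feasibility trial. The conclusion is only that such a table could not carry that reading. This is a cheap improvement, not a flaw that undermines the trial.

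**What to change.** At Visits 3 and 4, add seated blood pressure and heart rate to the existing hourly nausea, pain and Draize checks, and keep the seated and standing readings at visit start and end. Change Sections 7.4.1 and 7.4.2 and Appendix A together. Summarise, by treatment, the lowest on-treatment systolic and diastolic values and the largest fall from visit start. The clinical team should confirm the interval. The change concerns data collection only and sets no dose, threshold or treatment rule.

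The cost is about 7 to 8 extra cuff readings per visit, taken by staff already at the bedside, with minor inconvenience to the patient. If this is not adopted, state in the protocol and the report that the vital-signs summary does not describe blood pressure during dosing.
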